9.3.3 Pregnancies and pregnancy outcome

All available records related to pregnancies and pregnancy outcomes including diagnoses (based on ICD-10 coding tests and exams usually performed during a specific trimester) will be searched in databases, if available, as follows (see code list in Appendix 3).

- Pregnancies
 - Pregnancy records (date of record)
- Pregnancy outcomes
 - Outcomes of pregnancies (i.e., live births, termination, stillbirth, miscarriage, or recorded birth defect), if information is available in the data source

If information on the timing of the pregnancy is available (e.g., date of delivery, last menstrual period (LMP), trimester information), it will be considered for the estimation of the beginning of the pregnancy. The availability of such information may differ by data source.

In case no information is available permitting the analysis of the timing of the pregnancies, the method for calculating the timing of pregnancies, which is published for the specific data source, will be used. In case there is no approach published, the first pregnancy record minus 90 days, which mark the end of the first trimester and generally will be time of the pregnancy when a first check-up will have been performed, will be considered as the estimated start of the pregnancy. This approach was endorsed by the PRAC for another PASS (see for example Valproate, EUPAS11379).

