9.4.1.2 Germany – Collective of insurant from company health insurance funds

For this study, a collective of insurants from company health insurance funds will be used. The analysis will be done by Team Gesundheit, Gesellschaft für Gesundheitsmanagement GmbH, based in Germany.

Data are currently available from 2004 to 2016 (as of January 2018) and contain over 5 million insured patients representative of the entire insured German population with a coverage of about 6%. The privacy of patients in the database is protected at all times and the information cannot be used for re-identification of patients.

The database allows for the analysis of patient-level demographic and clinical characteristics, healthcare resource utilisation (e.g., number and/or duration of inpatient and outpatient visits), and dated prescriptions.

The coverage of pregnancies in women receiving health care services is high because all reimbursable services are comprehensively recorded in the claims data. The completeness of outcomes reporting varied depending on the type of outcome, e.g. an underreporting of induced abortions is possible (Mikolajczyk RT et al. 2013). Pregnancies will be identified in accordance with the approach published by Mikolajczyk et al.

The database also allows comparisons between patient and control groups with respect to specific utilisation of health care services.

Longitudinal pre-index and follow-up periods can also be defined according to the study requirements. Diagnoses and procedures are coded using ICD-10 (German modification), and include treatments that are reimbursed in accordance with the German law.

Among others, the following measures are available in the German database allowing demographic characteristics, treatments, healthcare utilisation and clinical outcomes to be assessed:

- Registration data including age, gender, insurance status, time insured, and region of residence
- Outpatient care data including ICD-10 diagnoses, physician specialty
- Inpatient care claim including ICD-10 diagnoses (up to 3 principal and 30 secondary diagnoses per stay), billed diagnosis related groups (DRGs, German classification), up to 30 OPS-Codes per stay, duration of hospitalizations, and medical department; drugs captured via OPS code
- Code of prescribed medications and related costs, PZN (Pharmazentralnummer) of prescribed medications, and date of prescription

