All medicines are prescribed electronically in Sweden. The National Prescription Register tracks the full details of all dispensed medications at individual patient-level in Sweden since July 1, 2005. Patients are followed longitudinally through their personal identification number, regardless of which pharmacy they visit. The National Drug Register is updated monthly and covers all sales from Swedish pharmacies.

The available data in the National Drug Register include:

- Patient demographics (age, gender, and residency)
- Prescription information (date of prescription, prescriber's specialty, WHO ATC code, and brand name)
- Dispatch information (dispatch date, product number, total dose dispatched, number of packages dispatched, and drug cost)
- Product information (Package size, formulation, etc.)

Information on prescribed dose is only documented in free text format where available, and days' supply is not recorded.

In Sweden, the online database on prescription held by the National Board of Health and Welfare provides the following information on the annual prevalence of Swedish women aged 15-49 years who filled at least one prescription for hormonal contraceptives in 2012-2017: ATC G02B contraceptives for topical use: 4.3-5.4%; ATC G03A hormonal contraceptives for systemic use: 22.4-26.1% (reference: prescription registry).

Of note, to gain access to the linked register an approval from the local ethical review board is necessary, whereby the research project and ethical aspects should be explained in a formal application. The ethics approval is dependent on the data being made publicly available in some form. Please see below for more detailed information on the information contained in each register.

The Medical Birth Register contains information on 97% to 99.4% of all pregnancies resulting in delivery in Sweden and is frequently used for quality work and for research (National Board of Health and Welfare, Sweden 2012; Olausson PO, 2002). The register contains detailed information about mothers and new-borns. However, pregnancies are only captured after 22 weeks. The identification and timing of pregnancies will be done according to published methodology (Stephansson et al. 2018).

Records on pregnancies are also documented in the National Patient Register regardless of the duration of pregnancy, but missing information regarding early termination needs to be taken into account.

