If the information on trimester, start date of pregnancy, or delivery/end of pregnancy date is available, the pregnancy will be considered exposed if at least one oral retinoid prescription was recorded in the period between the assumed dates of pregnancy start and delivery/end of pregnancy. In case information on pregnancy trimester or start date or delivery/end of pregnancy date is not available in the data source, a pregnancy will be considered as exposed to oral retinoids if at least one oral retinoid prescription was issued within 90 days before or within 180 days after the first record of a given pregnancy.

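### For pregnancies without recorded timing, section 9.7.3.3 omits the published-method step that section 9.3.3 requires and applies a fixed −90/+180-day window instead

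*Protocol*

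**What the plan says.** Protocol section 9.3.3 sets out three steps for dating a pregnancy.

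1. If timing information is recorded, "it will be considered for the estimation of the beginning of the pregnancy".
2. If none is recorded, "the method for calculating the timing of pregnancies, which is published for the specific data source, will be used".
3. Only then: "In case there is no approach published, the first pregnancy record minus 90 days, which mark the end of the first trimester", taken as the estimated start.

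Section 9.7.3.3 defines an exposed pregnancy in two branches.

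- Where trimester, start or end information is available, a retinoid prescription must fall "in the period between the assumed dates of pregnancy start and delivery/end of pregnancy".
- The other branch opens: "In case information on pregnancy trimester or start date or delivery/end of pregnancy date is not available in the data source". A pregnancy is then exposed if a prescription was "issued within 90 days before or within 180 days after the first record of a given pregnancy".

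The data-source sections refer to existing methods. For Sweden (9.4.3.1): "The identification and timing of pregnancies will be done according to published methodology". For Germany (9.4.1.2): "Pregnancies will be identified in accordance with the approach published". Section 9.4.1.1 mentions a published algorithm for pregnancy episodes in the French data. Section 9.4.2.1 describes a standardised calculation of the start of pregnancy in Spain, with a citation.

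**The concern.** Both sections govern a pregnancy whose timing is not recorded, and they prescribe different things. Section 9.3.3 sends it to the published method; section 9.7.3.3 sends it straight to a fixed window. Two analysts following the protocol could classify the same pregnancy differently. This could easily go unseen, because under section 9.6 the German and Spanish partners run their own analyses and return only completed tables.

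The choice between the two branches of 9.7.3.3 is also unclear. Both list trimester, start and end joined by 'or', so a pregnancy with a known start and no end satisfies both. Early losses are where this is likely to matter. Section 9.4.3.1 says that the Swedish birth register captures pregnancies only after 22 weeks and that information on early termination may be missing. Section 9.4.1.2 allows for under-reported induced abortions in Germany.

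The result affected is the number and incidence rate of exposed pregnancies. This is a secondary objective, but section 9.7.1 plans confidence intervals for its comparison, and it is the outcome closest to the harm that the programme is meant to prevent.

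**Working it through.** **Step 1: the two rules side by side**

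| Situation | Section 9.3.3 | Section 9.7.3.3 |
|---|---|---|
| Timing recorded | Use it to estimate the start | Prescription between assumed start and end |
| Not recorded, published method exists | Use that method | First record −90 to +180 days |
| Not recorded, no published method | Start = first record −90 days | First record −90 to +180 days |

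The rules conflict in the second row. In the third row their left edges coincide. Section 9.3.3 estimates only the start of a pregnancy; the +180 days in 9.7.3.3 are the only closing date offered for a pregnancy with no end.

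**Step 2: what the fixed window covers**

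The protocol states no figure to reproduce beyond the window itself, which is 90 + 180 = 270 days. Let g be the days from LMP to the first record and e the days from LMP to the end of pregnancy. The values of g and e, conception at LMP + 14 and term at day 280 are assumptions, not protocol figures.

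- Window days before LMP = max(0, 90 − g)
- Window days before conception = max(0, 104 − g)
- Window days after the end = 180 − (e − g); a negative value means that the window closes before the end

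| g | Days before LMP | Days before conception |
|---|---|---|
| 28 | 62 | 76 |
| 42 | 48 | 62 |
| 56 | 34 | 48 |
| 70 | 20 | 34 |
| 90 | 0 | 14 |

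| g | e | 180 − (e − g) | Meaning |
|---|---|---|---|
| 42 | 56 | 180 − 14 = 166 | 166 of 180 forward days fall after the end |
| 42 | 70 | 180 − 28 = 152 | 152 days after the end |
| 42 | 84 | 180 − 42 = 138 | 138 days after the end |
| 56 | 70 | 180 − 14 = 166 | 166 days after the end |
| 42 | 280 | 180 − 238 = −58 | last 58 days of pregnancy missed |
| 56 | 280 | 180 − 224 = −44 | last 44 days missed |

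The window can therefore be too wide at the front, too wide at the back after an early end, or too short for a term pregnancy recorded early. First records before day 90 are plausible here: Table 1 has pregnancy testing monthly, or ideally monthly, during treatment, and Annex 3.2 includes a code for confirmed pregnancy.

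**Step 3: which of these days the 9.3.3 hierarchy would remove**

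- A published method that dates the start removes the days before the estimated start. The last step of 9.3.3 does not, because it also goes back 90 days from the first record.
- A recorded or algorithm-estimated end removes the days after the end, provided the text says that such an end closes the window. Where neither exists, nothing removes them.

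**The case against.** The strongest reply is that the fixed window is only a fallback. The main rule in 9.7.3.3 works from assumed dates, and the natural reading is that these are the dates estimated under 9.3.3. With a method named for every source, and pregnancy listed as available for all four in Table 3, the window might rarely be used. A recorded end date already meets the first branch on its plain wording, so the 166-day example should not arise where the end is known. The statistical analysis plan, which is not shown, may settle the details, and section 9.9.2 already concedes that incomplete information on duration can misclassify exposure timing.

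Much of this stands. A reader might infer that 9.7.3.3 replaces the published methods for all pregnancies; it does not. A reader might also count every look-back day as a false exposure. Supply prescribed shortly before conception can run into pregnancy, and the 34 to 62 days before LMP for first records at days 28 to 56 remain under the last step of 9.3.3 too. The support in section 9.4 is also uneven: the French and German text speaks of identifying pregnancies, and only the Swedish text expressly covers timing as well.

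The reply does not remove the contradiction. Section 9.7.3.3 never says that assumed dates include those from a published method, and its fallback is triggered by information missing from the data source, which is exactly where 9.3.3 calls for that method. The overlapping 'or' conditions are in the text whichever reading is taken. The general caveat in 9.9.2 does not choose between the rules.

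**Conclusion.** Sections 9.3.3 and 9.7.3.3 conflict for pregnancies without recorded timing, and the branch conditions in 9.7.3.3 overlap. Read literally, a pregnancy that a named method could date would be classified by a 270-day window. That window can count prescriptions before the pregnancy began or after an early end, and can miss late exposure in a term pregnancy.

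The day counts are illustrations that rest on assumed record and end dates. How many pregnancies would reach the fallback cannot be computed from the protocol.

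It is tempting to infer that the update would bring earlier testing, hence earlier first records and more false exposures in the post-implementation period. Nothing in the protocol shows that first records would move, and the window errs in both directions, so the net direction is unknown. The outcome is secondary and the primary objective is untouched. The point is still worth correcting, because the rate is to be compared between periods with confidence intervals.

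**What to change.** In section 9.7.3.3:

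- State that the assumed dates follow the 9.3.3 hierarchy: recorded timing, then the source's published algorithm, then first record minus 90 days.
- Close the exposure window at any recorded or algorithm-estimated end, including termination and miscarriage.
- Reword the branch conditions so that each pregnancy meets only one, and say which closing date applies when the start is dated but no end is known.
- Restrict the −90/+180-day window to pregnancies with neither recorded nor algorithm-derived dates. Report their number by country and period, and give the results with and without them.

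The window should not simply be deleted, because those pregnancies would then have no closing date.

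The cost is wording and a little more analysis. No new data are needed, and the data-source sections already refer to the methods. The exposed-pregnancy count may change slightly.

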9.7.3.4 Meta-analysis

To account for any differences between the databases with regard to their format and to allow for differences in the population of patients treated with isotretinoin, acitretin, and alitretinoin, and differences in adherence to PPP measures in those populations, a meta-analytic approach will be used to combine the data. Specifically, drug- and country-specific estimates for the primary outcome measures will be assessed. In case of high heterogeneity between country-specific estimates for (a) certain active substance(s), an appropriate random-effect method will be used to derive a pooled estimate. In addition, the sensitivity of the overall pooled estimates to the inclusion or exclusion of certain country-specific estimates will be assessed. In some instances, it may not be appropriate to pool the data, and in such cases country-specific estimates will be excluded from the pooled estimate and presented separately.

9.7.3.5 Trends in the prescribing and monitoring practice of oral retinoids with respect to measures of the PPP

To identify ongoing trends in the countries of interest, ITS analysis using segmented regression will be performed in case the conditions for this analysis will be met (such as the number of time points in the pre-and post-implementation periods [at least 6 timepoints per period] and the number of observations per timepoint [at least 100] is available). Using ITS analysis, data will be evaluated at multiple time points before and after an intervention in order to detect whether or not an intervention had a significantly greater effect than any underlying trend.

The ITS analysis can assess the following key parameters:

- Proportion of episodes with contraception use for the month before treatment start
- Proportion of episodes with continuous concomitant use of contraception during the entire treatment episode
- Proportion of episodes with laboratory pregnancy tests at treatment start (up to 7 days before start date of oral retinoid prescription)
- Proportion of episodes with monthly laboratory pregnancy tests during treatment

A final decision on key parameters and time points for ITS analysis will be made based on results of analyses for primary outcomes. ITS analysis will be conducted for the outcomes only if sufficient data will be available for reliable results.

The analysis of outcome measures (key parameters) during the pre- and the post-implementation periods will be performed as follows (on example of concomitant use of contraceptives):

The definition and formula for calculation of outcome measure:

$$Concom_{prop_t} = \frac{NEpisodes.concom_t}{NEpisodes_t}$$

Where:

$N_{Episodes.concom_t}$: number of episodes with continuous contraception during time (t -1, t)

$N_{Episodes_t}$: total number of treatment episodes during time (t -1, t)

The following linear model will be defined and applied within a Poisson regression analysis. Effectiveness will be measured with the significance level of 0.05.

$$Concom_{prop_t} = \beta_0 + \beta_1 \cdot T + \beta_2 \cdot P_t + \beta_3 \cdot T \cdot P_t$$

In this model:

$Concom_{prop_t}$: concomitant use of oral retinoids and contraception at time t

T : time elapsed since study start in units of x-month periods

P_t : indicator variable coding pre- and post-intervention period of the RMM

β_0 : baseline level at T=0

β_1 : outcome change per unit time increase (=pre-intervention trend)

β_2 : level change following the intervention

β_3 : slope change following the intervention

For the Poisson regression, count data (i.e., $N_{Episodes.concom_t}$) will be used directly, and to account for the rates and to adjust for changes over time of total episodes of oral retinoids prescriptions with relevant prior medication, the natural log (ln) of the variable $N_{Episodes_t}$ will be included in the model as an offset parameter. In case of overdispersion, quasi-Poisson will be used. Durbin-Watson (DW) test will be applied to assess the presence of autocorrelation and Newey-West standard errors will be used at the identified order if autocorrelation will be detected.

The results will be presented graphically in the results section of the report. Parameter estimates, standard errors and p-values will be presented in a summary table.

9.7.4 Sensitivity analyses

In order to take into account that pregnancy tests might be recorded earlier than 7 days before oral retinoid treatment start the time period before the exposure start date will be expanded to one month in a sensitivity analysis.

In order to take into account that the old and the updated RMMs may co-exist during a period a sensitivity analysis will be conducted for the post-implementation period thereby excluding the first 6 months after distribution of EMs in the target countries.

9.7.5 Exploratory Analyses (If Applicable)

Not applicable

9.7.6 Handling of Missing Data

Due to the nature of real-world data, some data points might be missing from the databases for a number of reasons. The number and type of missing values will be recorded and reported in the final study report. Statistical calculations (i.e. the denominator) will be adjusted accordingly for the analysis.

Information on recommended daily dose may be not available from all data sources. The proportion of missing values will be described. However, the degree of completeness varies between databases. The missing information will be highlighted. In case dose recommendation is missing, dose information from the SPC will be used.

9.8 Quality Control

The study will use existing databases, which are being used widely for research. The study will be executed in line with all applicable regulations and guidelines – such as best-practice guidelines applicable to non-interventional DUS, including but not limited to the ENCePP Guide on Methodological Standards in Pharmacoepidemiology, the ENCePP Checklist for Study Protocols, and the Guidelines for Good Pharmacoepidemiology Practices of the International Society of Pharmacoepidemiology (ISPE GPP) as well as the specific IQVIA SOPs. All study programs, log files, and output files will be stored on the secure server. Where elements of the study are being conducted by a third party, the datasets and analytic programs will be stored according to the vendor's procedures.

9.8.1 Approaches for Validating the Results

The quality control for validating the results will be conducted at three levels:

- 1) At the statistical analysis level: all data management and statistical analysis programs developed and used in the analysis will be documented. All versions generated will be dated, kept with accompanying documentation and archived. The original database will be stored. A derived database will be created for the new versions of the data in order to include recoding and computing of new variables,

especially stratification of continuous variables, combination of modalities for categorical variables, calculation of composite indicators, etc.

- 2) At the results level, a data review will be done to ensure data integrity. A statistical analysis report including all the results will be provided for review and discussion. The final statistical report will take into account the reviewers' comments.
- 3) At the study level, all aspects of the study will be conducted according to the SOPs of IQVIA Real World & Analytics Solutions. The study documents have been approved by people competent in medical and safety areas of IQVIA. According to the SOPs, an independent review of the DUS results and report will be conducted by a person who was not in charge of their preparation.

9.8.2 Record Retention

The MAHs must maintain an adequate and accurate records to enable the conduct of the study to be fully documented, including but not limited to the protocol, protocol amendments, documentation of IRB/EC and governmental approval/notification (if required) and study reports.

Records and documents pertaining to the conduct of this study will be retained for at least 15 years after completion of the study. The length of storage can be extended based on MAH-specific SOPs or for the length of time required by relevant national or local health authorities, whichever is longer. After that period of time, the documents may be destroyed, subject to local regulations.

IQVIA will store study documentation on behalf of MAHs for 5 years, in accordance with IQVIA Standards and will transfer the documentation to the MAHs for long term archiving.

